6.1 Service Evaluation Study

The Phase 3 Service Evaluation will assess the real-life operational performance of the candidate triage tool, selected at the end of Phase Two, based on actual transport destinations.

Study setting and population

In Phase Three the most optimally performing candidate triage tool, determined from Phase Two, will be voluntarily implemented operationally in a major trauma network within each ambulance service. System-level accuracy, compliance, and usability will be evaluated. Consecutive patients of any age will be included if attended by EMS following injury over the 6 month study period. Patients transported to participating trauma networks from non-study EMS, transported to out-of-area hospitals, or where record linkage would not be possible will again be excluded. Patients from mass-casualty major incidents will again be excluded.

Implementation of the candidate triage tool

Introduction of the candidate triage tool will be conducted in partnership with participating trauma networks. Training will be provided to all relevant ambulance service staff using standard methods for implementing protocol changes within ambulance services (e.g. face-to-face sessions or on-line teaching packages). Major Trauma Centres and Trauma Units will be informed of changes to pre-hospital triage tools in advance.

Identification of injured patients and data collection

EMS and hospital data collection will be performed as described for Phase Two.

Data linkage, handling and record keeping

Data linkage, data handling and record keeping will be performed as described for Phase Two.

Consent procedures

In Phase Three an optimal candidate trauma triage tool will be selected by trauma networks for implementation. A service evaluation will subsequently be performed using routinely collected data to evaluate real life performance and compliance. As no additional data will be collected, and the triage tool will be applied to all patients presenting with injury, we will not obtain individual patient consent, but we will seek ethical approval from an NHS research ethics committee and CAG to analyse anonymised linked data.

Sample size calculation

Participating ambulance services estimate 150,000 calls for injury per 6 months across the included trauma networks, with TARN data suggesting that approximately 1,200 of these cases represent major trauma (ISS>15). Assuming, based on ASCOT criteria, a triage tool requires sensitivity of 95%, this sample size would provide a 95% confidence interval coverage of ±1.0% for the under-triage rate. Assuming a target specificity of 70% as per

ASCOT guidance, coding 3000 reference standard negative cases (sampling fraction of 2%) would give a 95% confidence interval coverage of $\pm 1.5\%$ for the over-triage rate.

Statistical analyses

The implemented triage tool will be scored using observed data, the presence of a trauma pre-alert recorded, and the actual transport destination collected. Compliance and real life performance of the implemented triage tool will subsequently be assessed. The reference standard will be the MATTS expert consensus definition of trauma with the potential to benefit from MTC care. Under/over-triage, sensitivity, specificity, predictive values, and c-statistics with their 95% confidence intervals (95% CI), will be calculated. The compliance of paramedic transport decisions with triage protocol results will be examined as a proportion with 95% CI. A priori sub-group analyses will examine tool performance in children and the elderly; and in penetrating and urban injury victims.

Safety reporting

In the MATTS Phase Three service evaluation study an optimal candidate triage tool will be voluntarily implemented by participating trauma networks. Adverse changes in the health of patients will be defined, monitored, recorded and reported according to CTRU SOP PM004 and Health Research Authority guidance for non-CTIMP studies. Adverse events (AEs) and serious adverse events (SAEs) related to major trauma triage will be recorded and reported. Table 1 details the definitions used.

Identification

Adverse health changes will be identified by paramedics during implementation of the triage tool and by research paramedics' review of EMS and hospital records. AEs will also be detected through review of ambulance service, hospital and trauma network incident reporting processes. Furthermore local investigators will report any additionally identified adverse health changes.

Management

All adverse health changes will be assessed for severity by an appropriately qualified member of the MATTS research team, or local clinician. It is their responsibility to review all documentation (e.g. patient records, laboratory and diagnostic reports) related to the event and determine seriousness according to the definitions stated in Table 1.

By definition, major trauma is a life threatening Illness that will result in hospitalisation, disability, or incapacity, and these outcomes will therefore not be classified as SAEs. If an AE is classed as non-serious, these will be recorded by the MATTS research team, and reported on aggregate to CTRU on a monthly basis.

If the AE is classed as serious, an SAE report form must be completed by the MATTS research team and sent to the CTRU within 24 hours of its discovery. The CI will then review causality, and expectedness to determine whether the SAE is related and/or is unexpected. Additional information may be requested from local research team members, research site staff, or GP, at a later date.

Documentation

SAE's deemed unrelated to the triage tool or study procedures will be recorded in the TMF only, and no further action will be taken.

All identified related SAE's will be documented in the participant's source medical records (if relevant) and entered into the study database, and followed up until resolution. A SAE form will be completed for each identified SAE and signed by the Cl. This will be kept in the study

master file and a copy sent to the research site for filing in the investigator site file. If further information is obtained at a later date regarding a SAE, the SAE report form will be updated.

Reporting

Reporting requirements are dependent on the seriousness of the adverse health change and categorisation as expected or unexpected:

- Related expected SAEs, will be reported in aggregate to the PMG, SSC and DMEC prior to each meeting; to the sponsor every 3 months; and to the REC in the Annual Progress Report. Expected SAEs will include: false negative and false positive triage tool results; changes in clinical status during prehospital transportation; expected disease progression (e.g. deteriorating level of consciousness following traumatic brain injury); normal symptoms of underlying injury (e.g. pain, bleeding, nausea); or death and disability from underlying major trauma unrelated to the MATTS triage tool.
- Unexpected SAEs related to the triage tool or study procedures require expedited reporting. The trial manager will inform the sponsor and relevant NHS R&D department; trauma network and will also inform the REC and DMEC within 15 days of notification using the Health Research Authority (HRA) serious adverse event form.

Figure 3 summarises the safety reporting procedures. SAE data will be reported to the trial governance groups and the Sponsor as aggregated data periodically. This will be monitored at management meetings and, if required, action in regards to safety will be decided. A DMEC will also monitor adverse event data and make recommendations to the Study Steering Committee (SSC) on whether there are any ethical or safety reasons why the study should not continue.

	Definition
Adverse Health Change Terminology*	Definition
Seriousness	
Adverse Event (AE)	An adverse change in health that occurs while a patient is taking part in a study
Serious Adverse Event (SAE)	 Any adverse event occurring while a patient is taking part in a study, that results in: Death Prolongation of Hospitalisation Other significant medical event
Causality	
Unrelated	An adverse change in health that occurs while a patient is taking part in a study which is not caused by or related to study interventions or procedures.
Related	An adverse change in health that occurs while a patient is taking part in a study, which is caused by or related to study interventions. An AE or SAE is considered related if the relationship between the event and trial treatments is:
	 Possible - There is some evidence to suggest a causal relationship. However, the influence of other factors may have contributed to the event (e.g. the participant's clinical condition, other concomitant treatments). Probable - There is evidence to suggest a causal relationship and the influence of other factors is unlikely, or Definite - There is clear evidence to suggest a causal relationship and other possible contributing factors can be ruled out.
Fundada da este	
Expectedness Unexpected	Any adverse health change that is NOT consistent with the known and expected adverse events of trial treatments i.e. it is not listed in the protocol or related documents/literature as an expected occurrence.
Expected	Any adverse health change that IS consistent with the known and expected adverse events of study interventions.
Severity*	
Mild	An adverse health change that does not interfere with routine activities
Moderate	An adverse health change that interferes with routine activities
Severe	An adverse health change that makes it impossible to perform routine activities

Table 1. Classification of adverse events *The term 'severity', is used to describe the intensity, and should not be confused with 'serious' which is based on participant/event outcome or action criteria. For example, a headache may be severe but not serious, while a minor stroke is serious but may not be severe.

Figure 3. Flow chart detailing safety reporting procedures for the MATTS study

ADVERSE CHANGE IN HEALTH OF MATTS SERVICE EVALUATION STUDY PARTICIPANT

• Adverse change in health related to major trauma triage or study procedures

	IDENTIFICATION AND RECORDING	
, , , ,	s (pre-hospital), research paramedics (er (incident reporting systems)	pre-hospital or in-

Details recorded in:

•The patient's case notes (if appropriate) •The study database

MANAGEMENT

• All adverse health changes assessed for seriousness by an appropriately qualified member of the MATTS research team.

•All SAEs reported to the CI; SAEs recorded on SAE form and reported to CTRU within 24 hours.

• CI reviews causality, and expectedness.

REPORTING		
Related Serious Adverse Event	Unexpected Related Serious Adverse Event	
Reported in aggregate to: •REC (Annual Progress Report) •DMEC (Prior to meetings) •SSC (Prior to meetings) •Sponsor (3 monthly)	Expedited reporting of individual SAEs within 15 days, using HRA SAE form, to: •Sponsor •Ambulance service, hospital R&D •REC •DMEC	

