- Sample size: TARN/EMS data suggests approximately 200 major trauma cases (ISS>15) per 4 months per trauma network. Assuming a target sensitivity of 95% as per American College of Surgeons Committee on Trauma (ASCOT) guidance, the total of 800 reference standard positive cases would give a 95% confidence interval coverage of 2% for sensitivity. EMS data suggests approximately 25,000 patients presenting with injury over 4 months per trauma network (total 100,000 across all 4 of the participating trauma networks). Assuming a target specificity of 70% as per ASCOT guidance, coding 2000 reference standard negative cases (sampling fraction of 2%) would give a 95%CI coverage of 2% for specificity. The total sample size of 2,800 cases would equate to an approximate total of 700 patients (200 major trauma cases and 500 non-major trauma cases) per network. This should be a manageable work load for research paramedics (approximately 9 cases to code per working day), while providing sufficient statistical power.

The following table presents the precision achieved for a range of observed sensitivities and specificities with the proposed sample size:

Estimated	Precisio	Level of	LCL	UCL	Reference standard
sensitivity	n	confidence			positive N=
0.97	0.0125	0.95	0.95 8	0.98 3	716
0.95	0.015	0.95	0.93 5	0.96 5	811
0.90	0.02	0.95	0.88 0	0.92 0	865
0.80	0.03	0.95	0.77 0	0.83 0	683
0.70	0.03	0.95	0.67 0	0.73 0	897
0.60	0.035	0.95	0.56 5	0.63 5	753
0.50	0.035	0.95	0.46 5	0.53 5	784
Estimated	Precisio	Level of	LCL	UCL	Reference standard
Specificity	n	confidence			negative
					N=
			0.96	0.97	
0.97	0.0075	0.95	3	8	1988
			0.94	0.96	
0.95	0.01	0.95	0	0	1825
			0.88	0.91	
0.9	0.0125	0.95	8	3	2213
			0.78	0.81	
0.8	0.0175	0.95	3	8	2007
			0.68	0.72	
0.7	0.02	0.95	0	0	2017
			0.57	0.62	
0.6	0.0225	0.95	8	3	1822
			0.47	0.52	
0.5	0.0225	0.95	8	3	1898

• **Outputs:** Optimally performing candidate triage tool identified by expert consensus, PPI and participating trauma networks.

c) Phase Three - Evaluation of System-Level Performance of Implemented Optimal Triage Tool.

A service evaluation characterising under/over-triage rates of the candidate triage tool when implemented operationally:

- Setting: Major trauma network within each of the West Midlands, Yorkshire, South Western and London Ambulance Services.
- Study population: Any patient attended by EMS following injury. Sub-group analyses of children (<16 years) and elderly patients (≥65 years).
- Study sample:

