 - Reference standard positive cases: Census sample of consecutive cases meeting MATTS reference standard /secondary reference standards, identified through augmented TARN processes.

- Reference standard negative cases: Random sample of cases presenting to EMS with injury. Appropriate patients identified using injury related working impression codes, use of major trauma interventions, hospital trauma team pre-alerts, and call priority.
- Outcomes: Under/over-triage rates based on actual patient destinations and observed hospital pre-alerts.
- Data collection: Linkage of pre-hospital and hospital variables using prospective EMS and augmented TARN data.
- Sample size: EMS/TARN data suggests approximately 300 major trauma cases (ISS>15) per 6 months per trauma network. Assuming, based on ASCOT criteria, a triage tool requires sensitivity of 95%, the total of 1,200 major trauma cases would give a 95% confidence interval coverage of ±1.0% for the under-triage rate. EMS data suggests approximately 37,500 patients presenting with injury over 6 months per trauma network (total 150,000 across all 4 of the participating trauma networks). Assuming a target specificity of 70% as per ASCOT guidance, coding 3000 reference standard negative cases (sampling fraction of 2%) would give a 95%CI coverage of ±1.5% for specificity.
- Evaluation of acceptability and usability to patients, ambulance services, and other important stakeholders using mixed-methods
- Cost-effectiveness of alternative triage tools using decision analytical modelling.

Project timetable: 31 month funded 3-phase research programme.

- Phase 1 Development Work: Permissions and set up, systematic review, retrospective cohort study, clinician focus groups, decision analytical modelling, and expert consensus process (10m). Conducted prior to the Phase 2 validation and Phase 3 implementation studies primarily considered in the current protocol.
- Phase 2 Validation Study: Prospective data collection, linkage and analysis (8m);
- Phase 3 Service Evaluation: Triage tool implementation, mixed methods assessment of performance, acceptability and usability (7m);
- Close-out: cost-effectiveness modelling, analysis and write-up (6m).

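### The Phase Three half-widths are stated as ±1.0% and ±1.5%, but the stated sample sizes give about ±1.2% and ±1.6%

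*Protocol*

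**What the plan says.** The Phase Three precision statement appears twice in the protocol, with the same figures.

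- **Section 6.1, Sample size calculation.** Of 150,000 injury calls in 6 months, "approximately 1,200 of these cases represent major trauma (ISS>15"). At an assumed sensitivity of 95%, "this sample size would provide a 95% confidence interval coverage of ±1.0% for the under-triage rate". The same paragraph takes 3,000 reference standard negatives (a 2% sample) at 70% specificity and gives ±1.5% for over-triage.
- **Scientific Summary, Phase Three sample size.** Here "the total of 1,200 major trauma cases would give a 95% confidence interval coverage of ±1.0% for the under-triage rate", and the 3,000 negatives "would give a 95%CI coverage of ±1.5% for specificity".

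The Scientific Summary also contains a Phase Two table, introduced thus: "The following table presents the precision achieved for a range of observed sensitivities and specificities with the proposed sample size". The proposed Phase Two sizes are 800 positives and 2,000 negatives. Each row of the table pairs a proportion and a precision with its own N. One row of the specificity half gives N = 1,825 for a proportion of 0.95 and a precision of 0.01.

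**The concern.** The Phase Two table and the Phase Three text treat the same calculation differently. The table requires 1,825 subjects to estimate a proportion of 0.95 to within ±0.01 at 95% confidence. The Phase Three text claims that precision, at that proportion and confidence level, from 1,200. Both statements cannot be right, and this can be seen without any calculation.

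What is at stake is the accuracy of a planning statement. Under-triage and over-triage are the Phase Three outcomes, and these half-widths are the precision that the protocol attaches to them. Someone approving or later citing the protocol would expect slightly narrower intervals than the study will produce.

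**Working it through.** **Inputs, all from the protocol**

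- Positives, Phase Three: n = 1,200 (300 per network × 4 networks); sensitivity p = 0.95.
- Negatives, Phase Three: n = 3,000 (2% of 150,000); specificity p = 0.70.
- Confidence level: 95%, so z = 1.95996 and z² = 3.8415.

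**Step 1. Identify the protocol's method from its Phase Two table**

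Formula: N = z² p(1 − p) / d², rounded up.

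- p = 0.95, d = 0.015: 3.8415 × 0.0475 / 0.000225 = 810.97, so 811. The table has 811.
- p = 0.95, d = 0.01: 3.8415 × 0.0475 / 0.0001 = 1,824.7, so 1,825. The table has 1,825.
- p = 0.70, d = 0.02: 3.8415 × 0.21 / 0.0004 = 2,016.8, so 2,017. The table has 2,017.

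The other eleven rows agree in the same way, so this is the protocol's own formula.

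**Step 2. Apply it to Phase Three**

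Half-width = z √(p(1 − p)/n).

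- Positives: 1.96 × √(0.95 × 0.05 / 1,200) = 1.96 × 0.006292 = 0.01233, or ±1.23%. Stated: ±1.0%. Ratio 1.233 / 1.0 = 1.23.
- Negatives: 1.96 × √(0.70 × 0.30 / 3,000) = 1.96 × 0.008367 = 0.01640, or ±1.64%. Stated: ±1.5%. Ratio 1.640 / 1.5 = 1.09.

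**Step 3. Numbers that the stated precision would need**

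- ±1.0% at 0.95: 1,825 positives, which is 1,825 / 1,200 = 1.52 times the planned number.
- ±1.5% at 0.70: 3.8415 × 0.21 / 0.000225 = 3,585.4, so 3,586 negatives, which is 3,586 / 3,000 = 1.20 times the planned number.

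**Step 4. Does another interval explain the stated figures?**

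| Method | 1,200 at 0.95 | 3,000 at 0.70 |
|---|---|---|
| Stated in the protocol | ±1.0 | ±1.5 |
| Wald (the protocol's formula) | ±1.23 | ±1.64 |
| Wald, continuity-corrected | ±1.27 | ±1.66 |
| Wilson | ±1.24 | ±1.64 |
| Clopper-Pearson | −1.39 / +1.16 | −1.68 / +1.64 |
| Wald with finite-population correction for the 2% sample | not applicable (census) | ±1.62 |
| Wald, 90% interval | ±1.03 | ±1.38 |

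Values are in percentage points. No row gives both stated figures. The 90% interval comes near the first but misses the second, and the text says 95%.

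**Step 5. Does rounding explain them?**

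The Phase Two text gives 2% for 800 positives at 0.95 (computed 1.51) and 2% for 2,000 negatives at 0.70 (computed 2.01). Rounding to the nearest half point would produce both Phase Three figures, but would turn 1.51 into 1.5 and not the stated 2. Rounding to whole points would produce both Phase Two figures, but would turn 1.64 into 2 and not the stated 1.5. No single rule of this kind yields all four.

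**Step 6. The Phase Two table heading**

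The listed N runs from 683 to 897 for sensitivity and from 1,822 to 2,213 for specificity, so the rows show the number required for a chosen precision. Six of the fourteen rows need more than the proposed size (811, 865, 897; 2,007, 2,017, 2,213) and eight need fewer. The largest listed N in each half, and the 0.90 sensitivity row, change as follows at the proposed sizes:

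- sensitivity 0.90, n = 800: ±2.08% (listed 2.0);
- sensitivity 0.70, n = 800: ±3.18% (listed 3.0);
- specificity 0.90, n = 2,000: ±1.31% (listed 1.25).

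**The case against.** The best defence is that the discrepancy has no consequence. Phase Three is a descriptive service evaluation: section 6.1 plans estimates with 95% confidence intervals and sets no hypothesis test, success threshold or stopping rule that uses a half-width. The 1,200 is the expected yield of consecutive cases over a fixed 6 months and was not derived from a precision target. It is itself approximate: it counts ISS>15, whereas the Phase Three reference standard is the consensus definition developed in Phase One. Against that uncertainty, 0.2 of a percentage point is small. All of this stands and it limits the severity, but it does not make the stated figures correct.

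It could also be said that the figures were rounded to the nearest half point. The protocol states no such rule, and its Phase Two text does not follow one.

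On the table, the defence is largely sound. Each row prints its own N, more than half the rows need fewer than the proposed size, and at the planning values the gap is trivial (811 against 800; 2,017 against 2,000). Only the heading is inaccurate.

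A reader might infer more than the protocol supports:

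- **That Phase Three is too small.** The protocol sets no minimum precision that the study must reach, so the larger numbers in the working show the size of the misstatement and are not a recruitment requirement.
- **That a precision guarantee to the funder or steering committee is broken.** The protocol says that the steering committee approves it. It does not present these half-widths as a commitment.
- **That Phase Three has no other planning basis.** It also gives case yields, call volumes, a sampling fraction and target accuracy.

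**Conclusion.** The two Phase Three half-widths are wrong as written, in both places where they appear. With the protocol's own inputs and formula they are ±1.23% and ±1.64%, against ±1.0% and ±1.5% stated. The true half-widths are 23% and 9% larger than stated; put the other way, the stated values fall short of the true ones by 0.233 / 1.233 = 19% and 0.140 / 1.640 = 9%.

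Severity is minor. The absolute errors are about 0.23 and 0.14 percentage points, and no design, test or decision threshold depends on them.

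The calculation assumes independent observations, the full 1,200 and 3,000 available for analysis, and true values of 95% and 70%. It makes no allowance for clustering by network, for exclusions or for unlinked cases, any of which would be expected to widen the intervals further. The protocol gives no figures from which to size these effects.

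**What to change.** In the Scientific Summary (Phase Three sample size) and in section 6.1 (Sample size calculation), change the half-width for 1,200 positives at 95% sensitivity to ±1.2%, and the half-width for 3,000 negatives at 70% specificity to ±1.6%. Keep both sample sizes.

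As optional wording, retitle the Phase Two table in the Scientific Summary as the number required for a given precision, or recompute its precision column at N = 800 and N = 2,000.

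The cost is a text correction in two places, plus the table if wanted. Recruitment, coding workload, timetable and analysis are unaffected; the stated precision becomes slightly less favourable.

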What is the problem being addressed?

The MATTS project addresses the research questions outlined in the HTA commissioned research brief: a national pre-hospital major trauma triage tool/process. Major trauma is an important and life-threatening condition caused by serious injury.[1] It has a bimodal age distribution with a first peak in the under-20s, and a second peak in over-65s; an age group where the burden of trauma continues to increase.[3] In 2012 major trauma care in England was reconfigured with the introduction of regional networks, aiming to concentrate seriously injured patients in specialist MTCs.[4] The bypass of non-specialist local hospitals ('non-MTCs') with less experience, resources and expertise, has been associated with improved patient outcomes; the correct identification of appropriate patients who may benefit from specialist MTC care is therefore critical.[2, 5, 6] The recent NICE trauma guideline recommends that pre-hospital triage tools should be used by EMS (i.e. the ambulance service) to identify which patients should be sent to MTCs.[7] However, research has suggested that existing triage tools are inaccurate, particularly in elderly patients, and NICE were consequently unable to support a specific tool.[8] Further research was therefore recommended to develop and validate a national trauma triage tool.

Why is this research important?

Major trauma is a major public health problem responsible for 3,000 fatalities, 8,000 patients with severe disabilities, £0.4 billion of immediate treatment NHS costs, and a £3.5 billion loss in economic output each year in England.[1, 9] Improvements in the management of major trauma, therefore, have the potential to improve greatly both health, and individual and societal wealth. In England, an estimated 20% of the annual 6.3 million 999 calls requiring an EMS response are due to injury,[10] but only a small fraction represents major trauma and identification is not always obvious at the scene of injury. Bypassing of patients without potential to benefit from MTC care ('over-triage') may waste the time, money and resources of ambulance services and MTCs; and may inconvenience patients and their families. Conversely, failing to recognise appropriate patients with serious injury ('under-triage') could result in transport to non-specialist hospitals, resulting in less effective treatment, increased harm including higher rates of mortality, and poorer recovery.

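### Section 6.1 exempts hospitalisation, disability and incapacity from SAE status by outcome rather than cause, so tool-related disability can bypass causality review; the expected-SAE list contradicts the exemption

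*Protocol*

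**What the plan says.** All of this is in Protocol section 6.1, Safety reporting.

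- **Management** has an assessor decide seriousness against Table 1. It then sets a blanket exemption, on the ground that "major trauma is a life threatening Illness that will result in hospitalisation, disability, or incapacity, and these outcomes will therefore not be classified as SAEs". No condition on relatedness to the tool is attached.
- **Management** then divides the events. For non-serious ones, "these will be recorded by the MATTS research team, and reported on aggregate to CTRU on a monthly basis". For serious ones an SAE form goes to the trials unit within 24 hours, after which "The CI will then review causality, and expectedness to determine whether the SAE is related and/or is unexpected".
- **Table 1** keeps three outcomes that make an event serious: death, plus "Prolongation of Hospitalisation Other significant medical event". Disability, incapacity and a new admission are not among them.
- **Reporting** sends related expected SAEs to oversight bodies in aggregate and reserves expedited reporting for SAEs that are both related and unexpected. Its list of expected SAEs includes false negative and false positive triage results, and also "death and disability from underlying major trauma unrelated to the MATTS triage tool".
- **Figure 3** starts from health changes related to triage or study procedures, then shows seriousness assessment, then the chief investigator's review of causality and expectedness.

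**The concern.** An outcome that the injury often causes anyway is hard to attribute. That is a reason to judge causality, not to settle the matter one step earlier. Here the exemption works at the seriousness step and is defined by what happened to the patient, not by why. A patient whose disability may owe something to a wrong triage result, and to the destination that followed, meets the exemption as fully as one whose disability is due to the injury alone.

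The protocol itself treats this kind of harm as a consequence of triage. Section 1 says that under-triage could send patients to non-specialist hospitals, "resulting in less effective treatment, increased harm including higher rates of mortality, and poorer recovery". Section 6.2.1 makes disability one of the outcomes by which triage strategies are compared. If the rule is followed as written, the safety record of the implemented tool may understate a harm that the programme expects under-triage to produce.

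**Working it through.** The documents state no figure to reproduce. The check is a reading of the rules in sequence, followed by arithmetic for scale.

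**Step 1: order of decisions.** Management and Figure 3 agree: seriousness is decided first; an SAE form follows only for serious events; the chief investigator's causality and expectedness review follows only from that form. Non-serious events go to the trials unit monthly in aggregate, with no causality step stated. Expedited reporting needs an event that is an SAE, related and unexpected. An event that fails at seriousness therefore cannot reach the later steps on the strength of that outcome.

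**Step 2: each outcome in the three places that classify it.**

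| Outcome | Management | Table 1 | Reporting |
|---|---|---|---|
| Death | not exempted | serious | expected SAE when from the underlying trauma and unrelated to the tool |
| Disability | not an SAE | not listed | expected SAE on the same terms as death |
| Incapacity | not an SAE | not listed | not named |
| New hospitalisation | not an SAE | not listed | not named |
| Prolonged hospitalisation | not separately addressed | serious | not named |
| False negative or false positive result | not addressed | not listed | expected SAE |

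Two conflicts follow. First, disability is not an SAE under Management, yet it is an expected SAE under Reporting. Second, the expected list belongs to the category of *related* expected SAEs, but its entry on death and disability is expressly for events *unrelated* to the tool. The Documentation text makes the second conflict practical: it records unrelated SAEs in the trial master file with no further action, whereas the Reporting list would send the same events in aggregate to the management group, steering committee, DMEC, sponsor and REC.

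**Step 3: who the rationale covers.** The reason for the exemption is a statement about major trauma. Section 6.1 includes every injured patient attended by the ambulance service. From its sample size text:

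- major trauma share: 1,200 / 150,000 = 0.008 = 0.8%
- remainder: 150,000 − 1,200 = 148,800, and 148,800 / 150,000 = 99.2%

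The 1,200 is a count of cases with ISS>15, which may differ from the count under the project's own consensus definition. The rationale does not describe the 99.2%, and the text does not say whether they are inside or outside the exemption.

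**Step 4: the group in which under-triage harm could arise.** At the 95% sensitivity used for the sample size, expected false negatives are 1,200 × (1 − 0.95) = 60. This counts under-triaged patients, not patients harmed. No rate of disability, incapacity or prolonged stay after a wrong triage result is given, so the number of events that would bypass review cannot be calculated.

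**The case against.** A reader might infer that most non-fatal harm from the tool can never reach review. The documents do not support that.

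- *Most* has no figure behind it. The national burden figures in section 1 describe injury as a whole, not harm due to triage.
- *Never* ignores routes that remain. Table 1 keeps "Prolongation of Hospitalisation" and a category for other significant medical events. A false negative result is itself listed as an expected SAE, so an under-triaged patient may reach the chief investigator by that path.
- Relatedness is not wholly ignored beforehand. Section 6.1 limits recording to events related to triage, and Figure 3 starts from the same condition.
- Exempted events are not lost. They are recorded and aggregated, the DMEC monitors adverse event data (sections 6.1 and 7), and the under-triage rate is itself a Phase Three outcome.

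A reader might also infer that all 148,800 patients without major trauma fall under the exemption. The sentence has major trauma as its subject and can be read as confined to it. The text leaves this open.

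These points limit the finding but do not remove it. The category for other significant medical events is a matter of judgement, and an assessor told that disability is not an SAE has a reason not to use it. Listing a false negative as an SAE does not make the patient's later disability one, and it pre-classes the case as expected, which keeps it on the aggregate route. The entry condition in Figure 3 means that an event already thought triage-related can still drop out at seriousness. For non-serious events the only specified reporting line runs to the trials unit.

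**Conclusion.** The point holds in a limited form. Because the exemption is by outcome and is applied before causality review, disability or incapacity to which a wrong triage result may have contributed can, as such, be classed as non-serious and miss both formal causality review and expedited reporting. It will not always be missed, given the remaining routes. Separately, and whichever way the exemption is read, section 6.1 contradicts itself on whether disability is an SAE and on whether unrelated events belong among related ones, so sites cannot apply it consistently.

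The number of affected events cannot be stated from the documents. The known scale is that the rationale fits about 0.8% of Phase Three calls, and that about 60 false negatives would be expected if the tool met its 95% target and major trauma is counted as ISS>15. The conclusion assumes that the exemption is applied as worded, without an unwritten exception for tool-related outcomes. It is a point that should be corrected before Phase Three safety reporting starts.

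**What to change.** Reconcile the Management and Reporting text of section 6.1, Table 1 and Figure 3 as follows:

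1. Make the exemption depend on cause. Hospitalisation, disability or incapacity is exempt only when judged due solely to the presenting injury. Where the triage result or the resulting destination possibly contributed, the event goes to the chief investigator for causality and expectedness review. Table 1 already counts a possible relationship as related, so no new standard is needed.
2. Bring Table 1 and Figure 3 into line with that rule, and state whether the exemption applies only to patients with major trauma.
3. Align the expected-SAE list. Remove unrelated events from the related category, and do not let harm after a false negative count as expected automatically. Without this, such cases would stay on the aggregate route even after the first change.

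This is a change of wording. Research paramedics already review ambulance and hospital records for adverse health changes, so no new data source is needed. The cost is more SAE forms and more reviews by the chief investigator. Their number cannot be estimated from the documents; within major trauma they would arise mainly among under-triaged patients.
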